Considering a baseline longitudinal prevalence of 13.2% (obtained from the control group of the PROMIS Mali study) with a standard deviation (SD) of 0.239 for the control group and an SD of 0.189 for the treatment group, a mean cluster size of 55 (anticipating a loss of follow-up of 15%), a statistical power of 80%, a type I error of 5% and an intra-cluster coefficient of 0.04, we need at least 42 clusters to detect a minimum difference of ~ 4.55 percentage points, , which is equivalent to a relative risk of 0.65.

Cohort 2 - Primary Outcome: recovery Rate

The aim is to include all URENAS and URENAM treatment data for children between 6 and 23 months of age. Using 2019 health district statistics, the total number of SAM and MAM cases (6-23 months of age) over 8 months of follow-up was estimated at 750 and 1,000 respectively.

Scenario with 45 clusters available (SAP version 1.0)

With 44 clusters that each have an average of 35 cases of SAM and MAM over a 7-month period, assuming a URENAS/URENAM cure rate of 79%, a statistical power of 80%, a type I error of 5% and an intra-cluster coefficient of 0.05, a minimum difference of ~9.0 percentage points in the URENAS/URENAM cure rate could be detected in children aged 6-23 months.

Scenario with 42 clusters available (SAP version 2.0)

With 42 clusters that each have an average of 50 cases of SAM and MAM over a 7-month period, assuming a URENAS/URENAM cure rate of 79%, a statistical power of 80%, a type I error of 5% and an intra-cluster coefficient of 0.05, a minimum difference of ~9.0 percentage points in the URENAS/URENAM cure rate could be detected in children aged 6-23 months.

Cohort 3 - Primary Outcome: Prevalence of Relapse

Scenario with 45 clusters available (SAP version 1.0)

We considered a 35% prevalence of relapse in children aged 9-17 months, three months after treatment completion (estimate obtained in the control group of the PROMIS Mali study). We need a minimum of 44 clusters with a mean cluster size of 20 (anticipating a 15% loss of follow-up), a statistical power of 80%, a type I error of 5% and an intra-cluster coefficient of 0.04 to detect a minimum difference of ~ 12.0 percentage points in the 9-18⁵ months age group.

Scenario with 42 clusters available (SAP version 2.0)

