⁹ Balegamire S, Siling K, Alvarez JL, Guevarra E, Woodhead S, Norris A. 2015. "A Single Coverage Estimator for Use in SQUEAC, SLEAC, and Other CMAM Coverage Assessments." *Field Exchange*, vol. 49

¹⁰ Barba, Francisco M., Lieven Huybrechts, and Jef L. Leroy. 2020. "Incidence Correction Factors for Moderate and Severe Acute Child Malnutrition From 2 Longitudinal Cohorts in Mali and Burkina Faso." *American Journal of Epidemiology* 189(12): 1623–27

used to assess the impact of the program. For cohort 3, data from October 2021 to February 2022 will be used to study the impact of the intervention on relapse.

Guiding principles and analysis strategy

Data will be analyzed on intent-to-treat basis. To allow for an analysis “as randomized” in the presence of missing data, we will impute missing data of the primary outcomes of the longitudinal study using a multiple imputation strategy under the *missing at random* assumption. Data management, data cleaning, and statistical analyses will be done using Stata 17.0 (Statacorp, USA). The statistical significance will be set at 5%. All statistical tests will be two-sided. The analysis of primary study outcomes will not be adjusted for multiple testing (n=3 primary study outcomes) given the data involved represent three distinct experimental and control study arms with each one primary study outcome.

We present results from non-adjusted and adjusted linear mixed effects regression models. The non-adjusted models use *health center catchment area* as a random intercept and sampling stratum as a fixed effect to represent the study design. Adjusted regression models further include as fixed effects the cluster baseline means (May-July 2021 period) of the outcome under analysis, month of enrollment into the study (cohort effect), child sex, child age, and primiparity. Furthermore, if any baseline household, caregiver or child characteristic is imbalanced (absolute difference of ~5pp) between study groups, we conduct an additional robustness analysis adjusting the analysis for this covariate.

Cohort 1 specific considerations

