For the analysis of the longitudinal prevalence of wasting (primary outcome), severe and moderate acute malnutrition and morbidity, the incidence of acute malnutrition and wasting we use mixed-effects Poisson regression models with robust estimation of standard errors to provide adjusted risk estimates. Results from non-adjusted and adjusted regression models will be presented as described under the paragraph on 'Guiding principles and analysis strategy'.

Continuous outcomes (such as WLZ, MUAC, LAZ) that are measured monthly will be regressed over calendar date using a linear mixed-effects model including *health center catchment area* and *child* as a random intercept and *follow-up time* as a random slope. For each model, we assess if the addition of a quadratic term of time improves the model fit significantly by applying a likelihood ratio test comparing the model with and without the quadratic term. To assess the specific impact of the intervention (SQ-LNS, MUAC screening and BCC) from enrollment at the age of 6 months to the end of follow-up, we assess the interaction between intervention allocation and time.

Dichotomous outcomes will be analyzed using linear probability mixed-effects models with robust estimation of the standard errors with *health center catchment area* as random effect and sampling stratum as fixed effect to demonstrate the impact of the intervention on the dichotomous outcome averaged over the follow-up period or at the end of the study. For repeated measures, to assess the specific impact of the intervention (SQ-LNS, MUAC screening and BCC) from enrollment at the age of 6 months to the end of follow-up (cohort 1), we assess the interaction between intervention allocation and follow-up time using a linear probability mixed-effects model with *health center catchment area* and *child* as a random intercepts and *follow-up time* as random slope.

Considerations for analysis

Baseline characteristics

For all variables measured, the available values at enrollment and collected from May to July 2021, i.e. before the start of the intervention, will be considered as baseline characteristics. The background characteristics of subjects who completed the study will be presented by intervention group. Following CONSORT guidelines, no statistical tests will be conducted comparing baseline characteristics between

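### With 42 clusters, robust standard errors and no stated small-sample correction or degrees of freedom, the two-sided 5% level is not held: Cohort 1 type I error is roughly 6-8% under a Wald z test

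*SAP*

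**What the plan says.** The general rules are in the SAP section 'Guiding principles and analysis strategy'. Significance is set at 5%, and "All statistical tests will be two-sided". The non-adjusted models take health center catchment area as random intercept and sampling stratum as fixed effect. The adjusted models add the cluster's baseline mean of the outcome, month of enrollment, child sex, child age and primiparity. The software is Stata 17.0.

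Under 'Statistical analysis methods', the longitudinal prevalence of wasting (the Cohort 1 primary outcome) is analysed with "mixed-effects Poisson regression models with robust estimation of standard errors". Dichotomous outcomes use "linear probability mixed-effects models with robust estimation of the standard errors".

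Under 'Sample Size', the current scenario for Cohort 1 states that "we need at least 42 clusters to detect a minimum difference of ~ 4.55 percentage points". 'Study design' gives four strata.

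The SAP names no small-sample variance correction, no t reference, no degrees of freedom and no permutation test.

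**The concern.** The arm effect is a between-cluster comparison, so the information about its standard error comes from 42 clusters and not from some 2,300 children (42 x 55 = 2,310). A sandwich variance is biased downwards when clusters are few, and more so as cluster-level terms are added. Referring the resulting statistic to a normal distribution then ignores the uncertainty in the estimated variance. Both effects make p-values too small and intervals too narrow.

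The SAP makes no multiplicity adjustment across its three primary outcomes, so the 5% level of each test is the only control of false positives. If that level is really 6 to 8%, the claimed control is not delivered. Because the reference distribution is not fixed, two analysts following the SAP could also report different p-values from the same data.

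**Working it through.** **Inputs from the SAP.** 42 clusters; mean cluster size 55; control longitudinal prevalence 13.2%; SDs 0.239 and 0.189; intra-cluster coefficient 0.04; power 80%; two-sided 5%; four strata.

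**Assumptions not in the SAP.** 21 clusters per arm (46 areas were randomized 23 to 23, but the split after the losses is not given); strata of 6, 10, 12 and 14 clusters; 4 to 7 visits per child; about 20 baseline children per cluster; coefficient of variation (CV) of cluster size 0 or 0.5.

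**Step 1: reproduce the plan's figure.**
- Design effect = 1 + (55 - 1) x 0.04 = 3.16. Children per arm = 21 x 55 = 1,155.
- Standard error = sqrt((0.239² + 0.189²) x 3.16 / 1,155) = 0.01594.
- Normal quantiles: (1.960 + 0.842) x 0.01594 = 4.47 points.
- t quantiles on 40 df: (2.021 + 0.851) x 0.01594 = 4.58 points.
- The SAP states about 4.55 points. The relative risk is (13.2 - 4.55)/13.2 = 0.655, against 0.65 stated.
- For the version 1.0 scenario (44 clusters of 35), t on 42 df gives 4.84 points, as stated; normal quantiles give 4.73.

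The stated figures are reproduced, and t is the closer match in both scenarios.

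**Step 2: closed form for the type I error.** Let G = 42 and let k be the number of cluster-level parameters: 2 for intercept and arm, 5 with stratum, 6 with the baseline mean added. Let c be 1 for the raw sandwich or G/(G-1) = 1.024 for the scaled one. For an equal-size cluster-level analysis the true size of a z test is

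P( |t(G-k)| > 1.96 x sqrt(c x (G-k)/G) ).

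With a t reference and no variance correction, 1.96 is replaced by the t(G-k) quantile.

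| Model | k | z reference | t(G-k), variance uncorrected |
|---|---|---|---|
| Arm only | 2 | 6.0-6.3% | 5.3-5.6% |
| Arm + stratum (SAP non-adjusted) | 5 | 7.1-7.4% | 6.2-6.5% |
| + cluster baseline mean (SAP adjusted) | 6 | 7.5-7.8% | 6.5-6.9% |

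Example for k = 5, c = 1: 1.96 x sqrt(37/42) = 1.840, and P(|t(37)| > 1.840) = 7.4%. The correct half-width uses t(37) = 2.026, so the z interval has 1.840/2.026 = 0.908 of its proper width. Over k = 5 and 6 and both values of c, the intervals are about 8 to 11% too narrow.

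**Step 3: simulation of the stated model.** A random-intercept Poisson model with cluster-robust standard errors was fitted under the null, 10,000 trials per setting (Monte Carlo standard error about 0.24 points).

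| Model | Equal sizes, z | Size CV 0.5, z |
|---|---|---|
| Arm + stratum | 6.6-7.0% | 7.0-7.3% |
| + baseline mean | 6.5-6.8% | 7.6-7.9% |

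With t(G-k) but only the G/(G-1) scaling, the same models gave 5.7 to 6.7%. A separate linear cluster-level simulation gave 6.1% under z, the low end of the range.

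**Step 4: which part is at fault.** Model-based (non-robust) standard errors with a z test gave 7.0 to 8.1% in the same models. Robust estimation is therefore not the source.

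**Step 5: does a correction restore 5%?** Scaling the variance by G/(G-k) and using t(G-k) gives 5.0% in closed form and 4.5 to 4.6% in simulation (5,000 trials, equal cluster sizes, Monte Carlo standard error about 0.3 points).

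**The case against.** The strongest reply is that the SAP is silent rather than wrong. It does not say that the sandwich is uncorrected or that z is used, and a sample size apparently planned with t may mean that a t-based analysis was intended. That stands in part: the 6 to 8% is conditional on a z reference. But the silence does not protect the level. A t reference alone still leaves about 5 to 7%, and holding 5% needs a step that the SAP does not mention.

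Second, the excess is modest and its size rests on assumptions. Stratum sizes, the arm split and cluster-size variation are not given, the upper end needs a size CV of 0.5, and child-level covariates and the multiple imputation were not simulated. This stands, and it is why a range is given.

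Three stronger readings may tempt a reader, and the document does not support them:
- *Robust standard errors are the mistake.* Step 4 shows that model-based errors with z do no better.
- *All three primary outcomes are shown to be affected.* Only Cohort 1 inputs were used. The dichotomous model is described after the Cohort 1 considerations, and its use for recovery and relapse is a plausible inference.
- *The stratum-specific results breach the 5% level badly.* Under 'Effect modification' those analyses are exploratory, interactions are judged at 10%, stratified results appear only if modification is indicated, and stratum sizes are not given.

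**Conclusion.** The concern holds in moderate form. Followed as written, the plan does not hold its two-sided 5% level for the Cohort 1 primary outcome. The type I error is roughly 6 to 8% with a Wald z test, or about 5 to 7% with a t reference and an uncorrected variance, and intervals are somewhat too narrow. This rests on 42 clusters split evenly, on assumed stratum sizes and cluster-size variation, and on analyses without child-level covariates or imputation. The extension to Cohorts 2 and 3 is by inference, on condition that the same models are used on the same 42 clusters. The excess is small but favours a false-positive result, and it is cheap to remove, so the SAP should be changed.

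**What to change.** Keep the models. Add to 'Guiding principles and analysis strategy' that tests and confidence intervals for the primary outcomes use one of the following, chosen in advance:

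- a small-sample-corrected robust variance (for example scaled by G/(G-k), or Kauermann-Carroll) with a t reference on the number of clusters minus the number of cluster-level parameters, which is 42 - 5 = 37 for the non-adjusted and 42 - 6 = 36 for the adjusted model; or
- a permutation test of cluster allocation within strata, which matches how the areas were randomized.

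The G/(G-k) scaling is the version checked above with equal cluster sizes. For Kauermann-Carroll with t, a separate simulation gave 4.9 to 5.0%. Its availability for a mixed-effects Poisson model in the named software should be confirmed before it is chosen. The SAP should also say whether the same rule applies to the Cohort 2 and 3 primary outcomes.

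The cost is slightly wider intervals and no change to data or models. In the Step 1 formula, t on 37 or 36 df gives a detectable difference of 4.59 points, against 4.58 on 40 df and about 4.55 stated, so the planned sample size approximately allows for it already.

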A population-representative longitudinal study design (**Cohort 1 or Main cohort**) was used enrolling children aged 6 to 6.9 months from May 2021 until November 2021. In addition, a second cohort (**cohort 2 or Treatment cohort**) was constituted consisting of all children admitted to MAM OTP (French: URENAM) and SAM OTP (French: URENAS) provided by first-line health centers and community health workers from May 2021 until February 2022. Finally, study field workers home visited a subsample of children three months after their discharge from SAM or MAM OTP to assess the impact of the intervention on post-treatment relapse rates (**cohort 3 or Relapse prevention study**). While the Main cohort study is an experimental study³, the Treatment cohort and Relapse prevention study are quasi-experimental in nature. The quasi-experimental character of these two sub-studies implies that the random character of the intervention and comparison group is not fully guaranteed. More precisely, children enrolled in the Treatment cohort may not be comparable between study groups because the BCC and SQ-LNS may prevent a proportion of the usual prevalence of wasting. Similarly, a higher screening coverage or screening by family MUAC may refer children with wasting with different characteristics as compared to those in the comparison group. Therefore, any impact or lack of impact of the NASG intervention to support the OTP services needs to be interpreted with caution, as it may be a result of both the intervention and any different characteristics of the enrolled samples of children. For the same reasons, the results of the relapse prevention study must be interpreted bearing in mind possible impacts of the preceding preventive BCC and SQ-LNS and improved screening and referral (studied in the main cohort), as well as possible impacts on the adherence and recovery rates of MAM and SAM OTP (studied in the treatment cohort).

Study outcomes

Primary study outcomes

1. The longitudinal prevalence of wasting in children enrolled at the age of 6 months followed monthly until the age of 12 months or until the end of the study, whatever comes first (**cohort 1 or Main cohort**). This indicator is defined for each child as the number of visits during which nutritional wasting is observed divided by the total number of monthly visits made (by the interviewers).

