- Wasting screening coverage defined as the proportion of children screened (using MUAC, WLZ or bilateral pitting edema) in the month prior to the monthly visit by the interviewers. Two sub-outcomes will also be concerned:
 - o Coverage of screening performed by NASGs within one month.
 - o Coverage of the family MUAC component, which is the screening performed by caregivers or family member within one month.
- The psycho-cognitive development of the children assessed via the DMC-II score at the end of the study.
- The linear growth rate including:
 - o Change in LAZ per month
- Ponderal growth by:
 - o The change in WAZ score per month
 - o The change in the WLZ score per month
 - o MUAC gain (change in MUAC per month)
- Longitudinal prevalence of childhood morbidity, i.e., acute respiratory infections, fever, diarrhea, and malaria, defined as the number of diagnoses of signs of these morbidities divided by the total number of monthly visits made by the survey teams.

- Caregiver knowledge of breastfeeding, complementary feeding, child health and hygiene, screening of wasting using MUAC, MAM and SAM OTP at the end of the study expressed as a cumulative total score and by subdomain.
- IYCF practices:
 - o Minimum dietary diversity of children during study follow-up and at the end of the study, defined as the proportion of children who consumed at least 5 of the 8 IYCF food groups (including breast milk) the day before the survey.
 - o Minimum meal frequency of children during study follow-up and at the end of the study, defined as the proportion of children who had 3 meals the day before the survey for breastfed children or 4 meals for non-breastfed children. The questions on feeding frequency exclude the consumption of SQ-LNS.
 - o Minimum acceptable diet at the end of the study, defined as the proportion of children with both minimal dietary diversity and minimal meal frequency on the day before the survey.
 - o Consumption of iron-rich or iron-fortified foods of children at the end of the study. The indicator will be calculated by excluding and including the SQ-LNS as an iron-fortified food.
- The adoption of practices recommended by NASGs and related to WASH, vaccination, and consumption of SQ-LNS at age of 12 months or at the end of the study.

For Cohort 2⁴

- Nutritional status (measured by WLZ and MUAC) at enrollment in SAM and MAM OTP (pooled), SAM OTP and MAM OTP in children 6-23 months of age.

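### The model for monthly growth outcomes names calendar date as its axis, follow-up time as its random slope and an undefined time in the arm-by-time term; one clock should be fixed

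*SAP*

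**What the plan says.** The text is in the SAP, Statistical analysis methods, under the Cohort 1 considerations.

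- **Fixed axis.** Monthly continuous outcomes "will be regressed over calendar date using a linear mixed-effects model".
- **Random part, same sentence.** Random intercepts for catchment area and child, with "follow-up time* as a random slope".
- **Curvature.** A likelihood ratio test decides whether a squared term in time is added. The time variable is not named.
- **Effect of interest.** The purpose clause and the start of the test read "from enrollment at the age of 6 months to the end of follow-up, we assess the interaction". The test itself is "we assess the interaction between intervention allocation and time", again with no clock named.
- **Dichotomous repeated outcomes, next paragraph.** The purpose is the same, but the clock is named: "we assess the interaction between intervention allocation and follow-up time using a linear probability mixed-effects model". The random slope there is also on follow-up time.

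Under Study design, the main cohort is described as "enrolling children aged 6 to 6.9 months from May 2021 until November 2021". Data sources restricts the impact data to August 2021 to February 2022. The outcomes served by the model are the growth rates under Secondary study outcomes, such as "Change in LAZ per month". Guiding principles and analysis strategy adds enrolment month and child age as main effects in the adjusted models only.

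**The concern.** Calendar date equals enrolment date plus follow-up time. If all children entered together, the choice of clock would not matter. Here entry spreads over seven calendar months, so a child seen in November may be at the first visit or the last.

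Read literally, calendar date is the only regression axis named. On that reading the unadjusted model lets each child's slope vary around a mean trend in follow-up time that the fixed part does not contain. A squared term would describe season more than the growth curve. The arm-by-time coefficient would draw partly on comparisons between early and late enrolees, and so would not be a clean estimate of the difference in monthly change since enrolment. Even without that reading, the analyst is left to choose between two models that give different answers.

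**Working it through.** The SAP gives no figure for this model, so there is nothing to reproduce. The check asks what an arm-by-calendar-date term would estimate.

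**Layout, from the SAP.** Enrolment month e = 0 (May) to 6 (November). Monthly visits at follow-up k = 0 to 6, cut at February 2022 (e + k ≤ 9). Calendar month c = e + k. Impact data have c ≥ 3 (August).

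**Assumed, not in the SAP.** One child per enrolment month and arm. True arm difference growing by δ = 0.03 z per month. Child SD 0.8 to 1.0, slope SD 0 to 0.20 z per month, residual SD 0.3 to 0.5. Cluster intercept omitted.

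**Correlation of the clocks.** 0.62 over all visits and 0.50 from August.

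**Why the term shrinks.** From August, the cohorts have:

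| Enrolled | Visits | Mean c | Mean k |
|---|---|---|---|
| May | 4 | 4.5 | 4.5 |
| June | 5 | 5.0 | 4.0 |
| July | 6 | 5.5 | 3.5 |
| August | 7 | 6.0 | 3.0 |
| September | 6 | 6.5 | 2.5 |
| October | 5 | 7.0 | 2.0 |
| November | 4 | 7.5 | 1.5 |

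Within a child, k rises by 1 per unit of c. Between cohorts, mean k falls by 1 per unit of mean c. Any weight on the between-cohort comparison therefore pulls the coefficient below δ.

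**Hand check, no random slope (child SD 1.0, residual SD 0.4).**
- The within-child sum of squares of c is Σ n(n² − 1)/12 = 5 + 10 + 17.5 + 28 + 17.5 + 10 + 5 = 93.
- The between-cohort terms n(mean c − 6)² are 9, 5, 1.5, 0, 1.5, 5, 9. Each is weighted by 0.16/(0.16 + n), which is 0.0385 for n = 4, 0.0310 for n = 5 and 0.0260 for n = 6. The weighted sum is 2 × (9 × 0.0385 + 5 × 0.0310 + 1.5 × 0.0260) = 1.08.
- Share of δ recovered = (93 − 1.08)/(93 + 1.08) = 0.98.

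**General case.** With V = σ²(child)·J + σ²(slope)·kkᵀ + σ²(residual)·I and fixed terms 1, arm, clock and arm × clock, the expected coefficients are (ΣXᵀV⁻¹X)⁻¹ ΣXᵀV⁻¹μ. The share of δ recovered over the whole variance range is:

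| Truth and data | Calendar date | Follow-up time |
|---|---|---|
| Effect from enrolment, all visits | 0.77–0.99 | 1.00 |
| Effect from enrolment, from August | 0.81–0.99 | 1.00 |
| Effect from the later of enrolment and August, from August | 0.89–0.99 | 0.96–0.99 |

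The loss grows with slope variance, because each child's own trend then carries less information. In the second row with child SD 1.0 and residual SD 0.4, the calendar-date share is 0.98, 0.97, 0.95, 0.91 and 0.86 for slope SD 0, 0.05, 0.10, 0.15 and 0.20. The lowest values come from child SD 0.8, slope SD 0.20 and residual SD 0.5.

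**Leakage.** The Cohort 1 considerations say that counselling before enrolment may have been greater in the intervention arm. Suppose there is no true effect on change, but the arm gap at enrolment grows by 0.03 z per enrolment month after August. In five variance combinations, the calendar-date term from August is then 0.0003 to 0.0034 z per month instead of 0. With follow-up time it stays within 0.0006 of 0.

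**Adjusted model.** Adding enrolment-month main effects left the calendar-date coefficient unchanged. Terms shared by both arms do not touch the arm contrast in this balanced layout.

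**The case against.** Five points can be made for the plan.

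1. *The interaction may already be on follow-up time.* The sentence says only time, its purpose runs from enrolment, the last time variable named before it is follow-up time, and the next paragraph uses follow-up time for the same purpose. This stands: the clock is undefined, not shown to be calendar date.
2. *The child intercept protects the estimate.* Within a child the two clocks differ by a constant. This also stands. A reader might infer that the arm-by-time term does not measure change since enrolment at all. That is too strong, since most of the true effect is recovered in every case tried.
3. *Calendar date has a rationale.* The programme starts on one date, and children enrolled from May to July begin follow-up before exposure. This stands in part: follow-up time then also loses a little. Calendar date did no better in that setting, and it lost more as slope variance rose.
4. *The adjusted models carry child age and enrolment month.* If age is taken at the visit, it nearly supplies the missing fixed trend, so the claim of no matching fixed effect is safe only for the unadjusted model. The SAP does not say which age is meant.
5. *The size rests on assumed variances.* It does, which is why only a range is given.

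**Conclusion.** The point holds as an inconsistency with a modest and conditional consequence. The SAP names two clocks for one model and a third, undefined one for the term that carries the treatment effect. If that term is on calendar date, the estimate is usually attenuated: by about 1% to 19% on data from August, up to 23% if all visits are used, and by 1% to 11% (against 1% to 4% with follow-up time) if the effect starts at the later of enrolment and August. These sizes rest on the assumed variances, equal monthly enrolment and a linear effect.

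A reader might also infer that the growth effects are certain to be diluted, or that the trial's main result is at risk. The document supports neither. Dilution requires the calendar-date reading, and the longitudinal prevalence of wasting is analysed with mixed-effects Poisson models that do not use this term. Only secondary growth outcomes are affected, so the priority is low.

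**What to change.** In the paragraph on continuous monthly outcomes, replace calendar date with follow-up time since enrolment. State that the same variable is used for the fixed trend, the quadratic check, the arm-by-time interaction and the random slope, as the dichotomous paragraph does for its interaction and slope. Handle season separately, through calendar month or the enrolment-month covariate already listed for the adjusted models.

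State also whether child age in the adjusted models is age at enrolment or at the visit. All children enter at 6 to 6.9 months, so age at the visit would be nearly collinear with follow-up time.

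The cost is a few words in the SAP and one variable in the model code. No new data are needed. If growth results have already been produced on calendar date, a refit on follow-up time can be reported beside them.

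### The Cohort 1 arm-by-time test of monthly growth does not state the level of its random slope or any robust standard errors; with a child-level slope alone it is anti-conservative if growth rates vary between health areas

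*SAP*

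**What the plan says.** The relevant text is in the SAP under Cohort 1, Statistical analysis methods.

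- **Continuous monthly outcomes.** "Continuous outcomes (such as WLZ, MUAC, LAZ) that are measured monthly will be regressed over calendar date using a linear mixed-effects model". Health area and child enter "as a random intercept and *follow-up time* as a random slope". The sentence does not say whether the slope varies by child, by health area or by both.
- **Tested effect.** To isolate the intervention's impact "from enrollment at the age of 6 months to the end of follow-up, we assess the interaction between intervention allocation and time".
- **Other outcome families in the same section.** Longitudinal prevalence and incidence use "mixed-effects Poisson regression models with robust estimation of standard errors". Dichotomous outcomes use "linear probability mixed-effects models with robust estimation of the standard errors". The continuous paragraph between them names no robust errors.
- **General rule.** Guiding principles and analysis strategy enters health area "as a random intercept and sampling stratum as a fixed effect to represent the study design", with no area-level slope.

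Study design defines the cluster, and so the unit of randomisation, as a health center catchment area. Secondary study outcomes lists monthly change in LAZ, WAZ, WLZ and MUAC.

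**The concern.** In a cluster-randomised trial, the standard error of the treatment effect has to carry the between-cluster variation of whatever is being compared. Here that is a slope. A health-area random intercept absorbs differences between areas in level, but not in growth rate. With a slope at child level only, the model treats the 42 × 55 = 2,310 child slopes as independent. Any variation in growth rate between areas is then missing from the interaction's standard error.

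Robust errors clustered on health area would repair this, but the text does not call for them in these models. At stake are false-positive claims, and confidence intervals that are too narrow, for four named secondary growth outcomes.

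**Working it through.** **1. The plan's own figure.** The SAP gives no sample size, slope variance or error rate for the slope test. Its nearest figure is the detectable difference for the longitudinal prevalence of wasting under version 2.0 ("an intra-cluster coefficient of 0.04, we need at least 42 clusters"; about 4.55 percentage points).

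- Sum of variances: 0.239² + 0.189² = 0.0928. Design effect: 1 + 54 × 0.04 = 3.16. Children per arm: 21 × 55 = 1,155.
- SE = √(0.0928 × 3.16 / 1,155) = 0.0159.
- Detectable difference = 2.80 × 0.0159 = 4.47 points with normal quantiles, or 4.58 with t on 40 df.

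The stated figure reproduces. It concerns the level of wasting prevalence and does not supply a slope ICC.

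**2. Inputs for the slope test.**

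- From the SAP: 42 areas (taken as 21 per arm), 55 children per area, two-sided 5%, enrolment May to November 2021, impact data August 2021 to February 2022, follow-up to 12 months of age. The May to November enrolment months then contribute 4, 5, 6, 7, 6, 5 and 4 visits, with enrolment assumed even.
- Assumed, because the SAP gives none: child intercept SD 0.95, area intercept ICC 0.04, child slope SD 0.10 per month, residual SD 0.30. Slope ICC means the area share of the true slope variance.

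**3. Method.** Take the generalised least squares estimate of the arm-by-time coefficient. Compare its model-based variance (no area slope, with that variance folded into the child slope) with its sandwich variance when areas do have their own slopes. With R the ratio of true to reported SE, type I error = 2 × (1 − Φ(1.96 / R)).

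**4. Results.** The reported SE is about 0.0056 per month throughout.

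| Slope ICC | Area slope SD | R | Type I error |
|---|---|---|---|
| 0 | 0 | 1.00 | 5.0% |
| 0.005 | 0.007 | 1.07 | 6.8% |
| 0.01 | 0.010 | 1.14 | 8.6% |
| 0.02 | 0.014 | 1.27 | 12% |
| 0.04 | 0.020 | 1.49 | 19% |

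Hand check at slope ICC 0.01: the omitted variance is about 2 × 0.010² / 21 = 9.5 × 10⁻⁶, against a reported variance of 0.0056² = 3.1 × 10⁻⁵. R ≈ √(1 + 0.30) = 1.14, as in the table.

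**5. Sensitivity.** Over child slope SD 0.06–0.15 and residual SD 0.2–0.4, type I error is 6–11% at slope ICC 0.01, 8–16% at 0.02 and 11–25% at 0.04.

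**6. A second definition.** If slope ICC instead means the area share of the variance of a child's *fitted* slope, measurement noise included, the inflation is the ordinary design effect 1 + 54 × ICC. At 0.005, 0.01, 0.02 and 0.04 this gives 8.2%, 11.4%, 17.4% and 27.0%. Simulation of a balanced six-visit design gave 8.3%, 11.5%, 18.8% and 24.2% (the last two from 500 runs), and 4.5% at ICC 0. Using calendar date or follow-up time as the time axis hardly mattered.

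**7. Does the remedy work?** In the same simulation, with area slope variance in the standard error and t on 40 df, type I error was 5.0–5.6% for slope ICC 0.005 to 0.04.

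**The case against.** The other side has several good points.

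- **Level of the slope.** A reader might infer that the SAP excludes a health-area random slope. It does not. Both levels are listed together and the slope's level is open. If the slope sits at area level or at both levels, the problem largely or wholly disappears. Child level is the natural reading because child is named immediately before it, but that remains an inference.
- **Robust errors.** They are unstated for the continuous models, not ruled out.
- **Size.** A reader might infer that type I error is well above 5% as a matter of fact. The documents do not support that, because the result depends on a slope variance that the SAP does not report. At a slope ICC of 0.001 it is only about 5.4%.
- **The 0.04.** It is tempting to borrow the sample-size ICC as a slope ICC. It was set for wasting prevalence, which is analysed by a Poisson model with robust errors. The 19% is therefore an illustration.
- **Binary outcomes.** It could be said that the repeated binary interaction model has the same gap. The paragraph opens with a rule for all such outcomes ("Dichotomous outcomes will be analyzed using linear probability mixed-effects models with robust estimation of the standard errors"), which plausibly carries over to the next sentence. Only confirmation is needed there.
- **Scope.** These are secondary outcomes.

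All of this stands and limits the claim. It does not remove the defect: one sentence permits both a model that respects the unit of randomisation and one that does not, and the more natural reading is the latter. Nor does the SAP give a reason to assume equal growth rates across areas. It stratified them because they differ in population, urbanity and remoteness.

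**Conclusion.** The concern holds in conditional form. The SAP does not fix the level of the random slope and names no robust errors for the continuous arm-by-time test. Two conditions are needed for harm: the slope is fitted at child level only, and growth rates vary between health areas. When both hold, the reported standard error is too small. Under the central assumptions it should be 7% larger at a slope ICC of 0.005 and 49% larger at 0.04, which puts type I error between about 7% and 19%. If areas do not differ in growth rate, there is no inflation.

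The variances and slope ICCs are assumptions. The direction and mechanism do not depend on them. This should be corrected, but it bears on secondary growth outcomes and not on the trial's primary conclusions.

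**What to change.** In Statistical analysis methods for Cohort 1, state that the continuous arm-by-time models carry a random intercept and a random slope on follow-up time at health-area level as well as at child level. Add the fallback: if that model does not converge, use standard errors clustered on health area with a small-sample correction for 42 clusters. For the repeated binary interaction model, confirm that the robust standard errors already stated apply and are clustered on health area.

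The cost is a sentence or two in the SAP and one extra term in the model code. Confidence intervals become somewhat wider where growth rates vary between areas, and change little where they do not.
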